Regarding psychiatric side effects, Rossi et al. report that in comparison with safety data for MDD, data for other psychiatric disorders are less complete; however, there is no evidence of a clinically different AE or SAE profile in other disorders, including where rTMS is applied for co-morbid depressive syndromes. (Rossi, et al., 2020) High-frequency rTMS has been reported to induce manic switch and delusions in patients with depression. (Sakkas, et al., 2003) However, while treatment emergent mania has been reported by Xia et al. for both low and high frequency rTMS in patients with uni- and bipolar depression following stimulation of the left

prefrontal cortex, the overall rate (13 cases) over 53 randomized controlled studies in depression appears to be not only low (0.84% versus 0.73% mania for active versus sham treatment, respectively), but even below natural switch rates in patients with bipolar disorders receiving mood stabilizers (2.3 – 3.45%). (Xia, et al., 2008) (Rossi, et al., 2020) Sub-manic symptoms of onset or worsening of insomnia, agitation, or anxiety are not uncommon among depressed patients receiving high-frequency rTMS in naturalistic settings. (Phillip, et al., 2015) Participants with MDD or bi-polar psychiatric disorders are excluded from the MERT-005-B study. While induced psychotic symptoms (Zwanzger reported one case of new delusional symptoms in a patient undergoing rTMS for MDD (Zwanzger, Robin, Keck, Rupprecht, & Padberg, 2002)), agitation, anxiety, insomnia and suicidal ideation have been reported (Janicak, et al., 2008) , Rossi et al. state that it is unknown whether such AEs are more frequent during rTMS compared to the natural course of the underlying psychiatric conditions. (Rossi, et al., 2020) They note that neither psychotic symptoms nor suicidal ideation have been described in normal subjects during or after rTMS and that there exists some evidence for an anti-suicidal effect of rTMS in MDD. (George, et al., 2014)

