- 15. Clinically significant medical illness, psychopathology, or other condition, that in the judgment of the Investigator might pose a potential safety risk to the participant or limit the interpretation of study results

Suicidality and Harm to Others

High suicide risk individuals will be ineligible as well as those with clinically significant psychopathology or other psychiatric disorders that may pose a safety threat to the participant. The U.S. Army Medical Command (United States Army Medical Command, 2014) screens individuals discharged from emergency departments and inpatient units. MEDCOM uses the Columbia Suicide Severity Rating Scale (C-SSRS) with triage points. The 6-item scale identifies ascending levels of risk, as subsequent items from 1 to 6 are endorsed as having occurred within the past month. Item 6 is related to actual preparatory activities, and it asks for additional time frame specificity, such as 1 week, 1 month, 3 months, and 1 year.

We will implement a suicide risk reduction plan for individuals found ineligible to participate in eTMS-PTSD-001 by virtue of suicidal ideation above a certain risk level. It is anticipated that some potential participants will have a measure of suicide risk, but these are some of the individuals for whom MeRT should be tested for benefit. It is therefore inappropriate to declare all persons with suicidal ideation ineligible. A triage plan tailored to the eTMS-PTSD-001will be implemented that considers the competing considerations of allowing enrollment of individuals with some measure of suicidal ideation yet excluding individuals at higher levels of risk, who require immediate intervention.

At the BL Visit, potential participants will be administered the C-SSRS. The C-SSRS incorporates findings from suicide literature and has prospective data that validates the scale's ability to identify risk probability ranges for potential future suicidal behaviors. The first 5 items of the scale divides responses according to whether the participant endorses an item within the past month or at a more remote time in the past. Items 1 and 2 refer to passive suicidal ideation

without intent or plan. Item 3 refers to whether a method has been considered, but intent is absent.

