PHQ-SADS, AUDIT, DAST-10, OCS, PSQI		х			x
CSSRS		Х			Х
Concomitant Treatments, Medications, Illicit Drug and Alcohol use		х	х	x	х
SEQ/AEs		Х	х	Х	Х
EEG		х			Х
МТ			Х		
eTMS			Х	Х	

TABLE 4: STAGE 1 SCHEDULE OF ACTIVITIES

Notes:

- 1. All eTMS treatments in Stage 1 are open-label active stimulation
- 2. Safety stage (Stage 1) study days are labeled SD to differentiate them from randomized stage (Stage 2) study days, labeled RD and from the open-label (Stage 2) days, labeled OD

TABLE 5: STAGE 2 SCHEDULE OF ACTIVITIES

	Enrol	llment		Study Treatment in Clinic	Follow-Up (F) Evaluations				
Procedures	sc	BL	Day 1	Days 2 through 35	(F1)	(F2)	(F3)		
Acceptable windows	RD-28 to RD-2	RD-28 to RD-1	RD+1	RD+2 to RD+21	RD+10 to RD+21	RD+71 to RD+77	RD+176 to RD+196		
Phone Screen	Х								
Informed Consent	Х								
MMSE, TMSs		Х							
Demographics		Х							
DHQ, BPI		Х			Х				
LEC-5, OSU-TBI-ID		Х							
Medical History/Physical, CGI		Х			Х	х	х		
Braincheck		Х	Х		Х				
VR-36, PCL-5		Х			Х	Х	Х		
PHQ-SADS, AUDIT, DAST-10, OCS, PSQI		х			Х				
CSSRS		Х			Х	х	Х		
Concomitant Treatments, Medications, Illicit Drug and Alcohol Use		x	х	x	х	x	x		
SEQ/AEs		Х	Х	Х	Х	х	X		
EEG		Х			Х				
MT			Х						
eTMS: (Active/Sham)			Х	Х					

Notes:

1. The F1 EEG may serve as the treatment-setting EEG for Open Label if conducted within 15 days of beginning OL treatment

TABLE 6: STAGE 2 OPEN-LABEL SCHEDULE OF ACTIVITIES

	Open-label eligibility	Open-Label Active eTMS in Clinic				
Procedures	EL	Day 1	Days 2 through 21			
Acceptable windows	Within 60 days of F1 completion	OD+1	OD+2 to OD+21			
Open Label Eligibility Review	Х					
Concomitant Treatments and Medications, MED, OCS		Х	Х			
SEQ/AEs		Х	Х			
EEG	X ³					
МТ		Х				
eTMS		Х	Х			

Notes:

- 1. All Stage 2 Sham-assigned participants who complete 75% of assigned study treatments during the randomized period may opt-in for up to 20 open label active eTMS treatments. They must continue to be safe to receive eTMS treatment as determined from data collected at the F1 data collection visit and prior to the first open label treatment.
- 2. The eligibility determination for open-label treatment (reviewed and signed by the Investigator) shall be made within 60 days of the completion of the F1 data collection in the randomized period.

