Veterans RAND 36-Item Health Survey (VR-36): The VR-36 is a self-report questionnaire surveying health-related quality of life and consists of 36 items. It was developed specifically for Veterans based on the Medical Outcomes Study RAND SF-36. (Measuring Health Preference, 2023) Items represent eight (8) domains, including: general health, mental health, energy, social functioning, physical functioning, bodily pain, disability (role limitations) due to physical problems, and disability (role limitations) due to emotional problems. Each of the subscales is scored on a range of 0-100, with higher scores indicating better function. Two summary scores, physical functioning (physical component score, VR-36 PCS) and mental functioning (mental component score, VR-36 MCS) are also generated. PCS and MCS summary scores are calculated using a t-score transformation that is normed to a general U.S. population, such that scores >= 50 indicate better-than-average functioning, and scores < 50 indicate diminished functioning. For both, standard deviation is 10 and MCID is 7. Norms updated per Selim (2009) for the general population use cutoffs of 51.4 (PCS) and 49.0 (MCS). Veteran norms based on a VA sample are: MCS=35.2 and PCS = 43.6.

MMSE: The MMSE is a rapid screen for cognitive function that is widely used among populations at risk for cognitive dysfunction due to age or neurologic condition. It will be given as part of the physical examination to evaluate for neurological disorders that may affect capacity for treatment consent or increased risk for side effects that would require closer monitoring. Administration takes approximately 5-10 minutes. Total scores range from 0-30, with higher scores indicative of better function.

C-SSRS: The C-SSRS will be used to identify persons deemed to be at too elevated of a risk of suicide to be included in the study and whether they need assistance. The Columbia Suicide Severity Rating Scale is a semi-structured interview to identify suicidal ideation and behavior. Assessment of suicidal behavior ranges from preparatory acts to suicide attempt (distinguished

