 - $\circ~$ Short-term. Resolves in the first 1-2 days of the rapy.

- No long-term implications.
- Treatment emergent mania/hypomania
 - \circ Sponsor's clinical use history ~5%.
 - Hypomania is much more common than mania. Often a secondary effect to improved symptoms.
 - Short term. Resolves in the first week of therapy.
 - No long-term implications.
- Anxiety/depression
 - Sponsor's clinical use history showed slight anxiety in ~5% of patients generally occurring in patients responding positively to therapy as awareness of their own behavior develops.
 - rTMS: Very rare in general. Observed when stimulation of RPFC and LPFC (Pascual-Leone, Catalá, & Pascual-Leone, Lateralized effect of rapid-rate transcranial magnetic stimulation of the prefrontal cortex on mood, 1996) (George, et al., 1996) which is not used in the present trial.
 - Short term. Resolves within the second week of therapy.
 - No long-term implications.
- Cognitive changes
 - Sponsor's clinical use history ~5% report an alteration to cognition, associated with fatigue following therapy.
 - rTMS: No evidence of long-term adverse effect on cognitive, perceptual, or motor functions in general (Pascual-Leone, et al., 1993) (Wassermann E. M., 1998)
 - Short-term. Resolves in the second week of therapy.
 - No long-term implications.
- Insomnia
 - \circ Sponsor's clinical use history ~3%.
 - Some patients nap following treatment, which disrupts sleep. Some report a shorter period of sleep initially with an early wake up.
 - \circ Short term. Resolves within the first week of therapy.
 - \circ No long-term implications.
- Dizziness
 - \circ Sponsor's clinical use history ~3%.
 - Patients may feel very relaxed during therapy, and experience mild light headedness when standing afterward.
 - Resolves by asking subject to remain seated and stand slowly, or by giving patient water to drink.
 - Short-term. Resolves in the first 1-2 days of therapy.
 - No long-term implications.
- Auditory effects
 - \circ Sponsor's clinical use history ~3%.

- rTMS: Effects on hearing are very rare. Transient rise in auditory threshold or tinnitus in a small number of cases in general (Pascual-Leone, et al., 1992) (Pascual-Leone, et al., 1993) (Loo, et al., 2001) (Boutros, Gueorguieva, & Hoffman, 2002) (Anderson, et al., 2006).

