
Stage 2

Stage 2 of the trial is intended to investigate efficacy and safety of the procedure in the target population. The primary efficacy outcome is a measure of PTSD symptom severity. PTSD symptom reduction will be calculated as the arithmetic reduction in PCL-5 scores between BL and F1. See the above Data Collection section for a description of this assessment.

Safety will be characterized by adverse event incidence, relatedness, severity, type, subsequent treatment/intervention required, and resolution status.

SAMPLE SIZE CONSIDERATIONS FOR STAGE 1

A convenience sample size of thirty (30) will be treated in the safety pilot stage in order to detect common adverse effects or safety concerns.

SAMPLE SIZE CONSIDERATIONS FOR STAGE 2

Sample size assumptions:

[figure not shown]
- Design variable is change in PCL-5 between BL and F1.
 - Mean in first responders = 38.73 (SD = 18.68) (Morrison, Su, Keck, & Beidel, 2021)
 - Primary outcome clinically important difference = 15(10-20) (U.S. Department of Veterans Affairs, 2022)
- Planned estimated effect size +0.8 SD_{difference}, for a difference in Active eTMS versus Sham eTMS group mean pre-post PCL-5 scores = 15, with pooled SD_{difference} = 18.68
- Assignment ratio =1:1 for Active eTMS vs. Sham eTMS
- 10% loss to followup

- Type 1 error = 0.05 (2-sided)
- Statistical power = .985
- Method of calculation Sample size and power for given detectable difference between two mean difference scores using Student's t-test according to method of Dupont & Plummer

Sample size requirements:

- Total completers: 108 (90% 54 per group) See Figure 2 below
- Total to be randomized:120 (60 per group)

FIGURE 2: Primary efficacy outcome, PCL-5. Statistical power by number of completers per treatment group for Type 1 error 0.05 (.985) and 0.01 (.938)

DATA AND SAFETY MONITORING BOARD

A Data and Safety Monitoring Board (DSMB) comprised of at least 3 **independent** subject matter, medical, clinical trial methods, and biostatistics experts will be constituted to review the protocol, recruitment progress, site performance, study conduct, and safety data. The Board will request analyses, and will make recommendations regarding study continuation, amendment, or termination, as well as the advisability of adding up to 3 additional research sites.

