Adverse events (AEs) will be summarized using MedDRA terms. AEs will be listed and summarized by system organ class, preferred term, incidence, severity and duration. Monthly safety summaries will be made for all study participants and listed by site and study treatment assignment and distributed to the Study Chair and Principal Investigator, who also will receive SAE reports in real-time. These listings will be produced for every DSMB meeting. The DSMB, the Study Chair and Principal Investigator will not be blinded to treatment assignment for any AE-related data.

STATISTICAL ANALYSIS PLAN FOR STAGE 2

Statistical Analysis Software

Statistical analyses will be performed using software such as the SAS® system, IBM SPSS, or EXCEL.

Analysis Populations

Two analysis populations are defined for Stage 2:

• The Intent-to-treat (ITT) analysis population includes all eligible and randomized participants

• The Per-Protocol (PP) analysis population includes all participants in the ITT population who (1) had all efficacy evaluations at the major study time points defining the primary outcome comparison, i.e., BL and F1, (2) who had no major protocol deviations, and (3) who received at least 75% of assigned blinded study treatments

Analysis of Safety

Adverse events (AEs) in Stage 2 will be summarized using MedDRA terms. AEs will be listed and summarized by system organ class, preferred term, incidence, severity and duration. Monthly safety summaries will be made for all study participants and listed by site and study treatment assignment and distributed to the Study Chair and Principal Investigator, who also will receive SAE reports in real-time. These listings will be produced for every DSMB meeting. The DSMB, the Study Chair and Principal Investigator will not be blinded to treatment assignment for any AE-related data.

Analysis of Efficacy

The tests of the primary and secondary efficacy outcomes will be hierarchical in order to constrain Type I error. If the test of the primary outcome shows a significant beneficial effect with a two-sided p-value ≤ 0.05 , the secondary efficacy outcome analysis will be conducted at a two-sided alpha = 0.05 level. If alpha has been spent in DSMB efficacy monitoring, the alpha level apportioned to the primary results analyses will be accordingly reduced.

Primary outcome efficacy analysis

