Poolability over study sites will be separately assessed. In a separate analysis the association between the primary endpoint and the study site will be explored. Both the main effect of study site and the interaction between study site and treatment group will be explored.

Additional Analyses of the Primary Outcome

Exploratory responder analyses will be conducted. To determine whether a greater percentage of Active-treated participants respond to study treatment than Sham-treated participants, the binomial z-test will be used to compare the Active-treated group to the Sham-treated group at a number of percentage reductions in PCL-5 scores as candidate values of a successful treatment response. A range of percentage reduction values will be investigated as possible discriminating values to assist in designing future trials regarding sample size justification and power analysis, should a trial in future be designed with a responder analysis as the primary outcome or a secondary outcome.

Other participant reported outcomes analyses

Other participant reported outcomes, including assessment of blinding, will be analyzed according to their level of data (e.g., quantitative, rank order, or categorical) and validity of statistical assumptions required (e.g., homoscedasticity and normality).

Electrophysiological data analyses

Quantitative EEG data collected at BL and F1 will be stored on hard disk and analyzed offline. Raw data of each record will be visually inspected to reject significant artifact contamination. Selective data will be further analyzed by fast Fourier transform (FFT) routine to yield four consecutive frequency bands – delta (0.5-4 Hz), theta (4-8 Hz), alpha (8-13 Hz) and beta (13-35 Hz). Power density of each frequency band of each channel will be used to measure the EEG changes after treatment. Statistical analysis will include data reduction by initial factor analysis. Difference between treatment groups at each recording time will be tested by repeated measures and regression of number of treatments by channel. It is anticipated that successful treatment will result in reductions in low frequency rhythms and increases in peak alpha frequency and correspondent narrow-band density. These changes in EEG variables will be further correlated with clinical and cognitive data to explore the hypothesis that EEG parameters could be a biomarker for PTSD.

STUDY SITE MONITORING

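### C-SSRS and Braincheck are collected after baseline, but the safety definition and safety analysis cover coded adverse events only, so no comparison of C-SSRS results between arms is specified

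*Combined protocol and SAP*

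**What the plan says.** **Collection.** In "TABLE 5: STAGE 2 SCHEDULE OF ACTIVITIES" the C-SSRS is marked at BL, F1, F2 and F3, and Braincheck at BL, Day 1 and F1. Table 4 has the C-SSRS at BL and F1 in Stage 1, and Braincheck at BL, Day 1 and F1.

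**Definition of safety.** Study Outcomes, Stage 2: "Safety will be characterized by adverse event incidence, relatedness, severity, type, subsequent treatment/intervention required, and resolution status".

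**Safety analysis.** Analysis of Safety, Stage 2: "AEs will be listed and summarized by system organ class, preferred term, incidence, severity and duration". The listings are by site and treatment assignment and go to every DSMB meeting. The Stage 1 plan has the same content. Neither instrument is named in any statistical section.

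**Stated role of the C-SSRS.** Data to be collected: "The C-SSRS will be used to identify persons deemed to be at too elevated of a risk of suicide to be included" (the sentence adds identifying who needs assistance). The entry describes it as a semi-structured interview.

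**Why these domains matter.** The section on suicidality explains that some people with ideation should be enrolled: "It is therefore inappropriate to declare all persons with suicidal ideation ineligible". The rTMS background says that "agitation, anxiety, insomnia and suicidal ideation have been reported". Under anticipated adverse device effects, about 5% in the sponsor's clinical use "report an alteration to cognition, associated with fatigue following therapy".

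**General clauses.** "Other participant reported outcomes, including assessment of blinding, will be analyzed according to their level of data" is limited to participant-reported outcomes. The synopsis says that exploratory outcomes are tested as appropriate and names none. Electrophysiological data analyses correlates EEG changes with clinical and cognitive data.

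**The concern.** The plan collects a dedicated suicidality interview and a cognitive test battery in both arms, then states a definition of safety that includes neither. The safety conclusion on these two domains would rest on events that someone chose to record.

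The gap is wider for suicidality. The protocol deliberately admits people with some ideation and says they are among those in whom benefit should be tested, yet no planned analysis looks at change in ideation. The background also argues that psychiatric events in rTMS trials reflect the population rather than the stimulation. A by-arm C-SSRS comparison at F1 bears directly on that argument and could support it. In Stage 1, where safety is the primary outcome and informs the DSMB's recommendation on Stage 2, the specified DSMB listings contain adverse events only.

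**Working it through.** **1. Does any provision reach the two instruments?**

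| Provision | C-SSRS | Braincheck |
|---|---|---|
| Study Outcomes, Stage 2 (safety) | no, adverse events only | no |
| Analysis of Safety | no, coded adverse events only | no |
| Other participant reported outcomes analyses | no, it is an interview | no, it is a performance test |
| Synopsis, exploratory outcomes (Blinding section: self-administered, electronic capture) | does not fit an interview | might fit a computerised test |
| Electrophysiological data analyses | not named | correlation with EEG, no arm contrast |

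**2. Does the adverse event route fill the gap?** The side-effects questionnaire (SEQ) prompts for expected adverse reactions. Its items are not shown; I assume they follow the anticipated-effects list. That list includes cognitive changes and anxiety/depression, but not suicidal ideation. Adverse Event Assessment counts a worsened pre-existing condition as an event, but no change in C-SSRS triggers a record. The safety section also says that disease progression is not to be treated as a serious adverse event, which leaves room for judgement on worsening ideation.

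**3. The plan's sample size.** Inputs: difference 15, SD 18.68, 54 completers per arm, two-sided test. 15/18.68 = 0.803. Noncentral t power is 0.9852 at alpha 0.05 (stated .985) and 0.9371 at 0.01 (stated .938). 108/0.9 = 120 randomised, 60 per arm. These figures reproduce and are not in dispute. The Study Design section gives 140 randomised (70 per arm), so both are used below.

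**4. Suicidality SAEs, for scale only.** The active-arm rates in the protocol's Table 1, among trials reporting any, are 0.6%, 1.3% and 3.7%. Expected count = n × p; chance of none = (1 − p)^n.

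- n = 60: 60 × 0.006 = 0.36 and 60 × 0.037 = 2.2; 0.994^60 = 0.70 and 0.963^60 = 0.10.
- n = 70: 0.42 and 2.6; 0.66 and 0.07.

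These are serious-event rates. The documents give no rate for all coded ideation events or for emergent ideation on the C-SSRS.

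**5. What a by-arm C-SSRS table could show (rates assumed).** With 54 per arm, 5% against 10% gives a 95% half-width for the risk difference of 1.96 × √(0.05×0.95/54 + 0.10×0.90/54) = 0.099. Two-sided Fisher power is about 7% for 5% vs 10%, 28% for 5% vs 15%, 56% for 5% vs 20% and 79% for 5% vs 25%. Zero events in 54 excludes a rate above 1 − 0.05^(1/54) = 5.4% (one-sided 95%).

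**6. Braincheck.** The difference detectable with 80% power at 54 per arm is (1.960 + 0.842) × √(2/54) = 0.54 SD; the 95% half-width is 0.38 SD. If 5% of the active arm declined by a full SD (assumed), the arm mean would move 0.05 × 1 = 0.05 SD, about a tenth of that. A comparison of means alone would miss such an effect.

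**7. Timing.** F1 falls at RD+10 to RD+21. Open-label treatment may start up to 60 days after F1, so as late as RD+70 to RD+81, while F2 is RD+71 to RD+77. At F2 and F3 the sham arm is therefore a mixture; F1 is the only clean randomised contrast. The suicidality section also describes a past-month recall for the first five C-SSRS items. Taking a month as 30 days, an F1 interview would reach back about 30 − 21 = 9 to 30 − 10 = 20 days before treatment.

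**The case against.** The strongest reply is that the plan already has a working safety system. Adverse events include observed problems and worsened conditions, are solicited at every treatment and follow-up visit, and are listed by assignment for the DSMB. Staff are trained to recognise suicidal ideation. The DSMB may request analyses and is to consider other endpoints before stopping for efficacy or futility. F1 data, which include the C-SSRS, inform open-label safety eligibility (Table 6, note 1), so the instrument is not used only at entry. All of this stands. The DSMB's power is discretionary, though, and none of these provisions puts C-SSRS results into the trial's safety analysis.

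Several stronger readings are tempting, and the documents do not support them:

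- A reader might infer that ideation and cognitive decline go wholly uncompared between arms. Recorded events are shown by arm, cognitive change may be prompted by the SEQ, and the synopsis clause might reach Braincheck.
- A reader might infer that the suicidality count will be near zero whatever the device does. The rates in step 4 are SAE rates, and at 3.7% there is a 90% chance of at least one event.
- A reader might infer that ideation is an acknowledged device effect. It appears in the background and the emergency plans, not in the anticipated-effects list. The background sentence goes on to say that it is unknown whether such events exceed the natural course of illness.
- A reader might infer that the trial enrols people at high suicide risk. Past-month intent, preparatory acts within six months and any lifetime attempt are all excluded.

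It is also fair that the added tables would be imprecise, and that the cognitive effect described is short-lived and may have resolved by F1.

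**Conclusion.** The point holds in a limited form. Safety is defined and analysed through coded adverse events, no C-SSRS comparison is specified, and the general clauses do not reach an interview-based instrument. For Braincheck the gap is less certain, because the exploratory clause might cover it, but no safety use is stated. Emergent ideation can appear in the results, but only if someone records it as an event.

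The size of any missed effect cannot be computed, because the documents give no C-SSRS rate; the 0.4 to 2.2 expected SAEs only indicate how few serious events to expect. The conclusion rests on reading the outcome definition as complete and on the SEQ following the anticipated-effects list. The primary analysis, sample size and clinical procedures are unaffected. The change is worth making because it is cheap and bears directly on what the trial can say about safety.

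**What to change.** Amend Study Outcomes (Stage 2) and Analysis of Safety so that safety covers adverse events, C-SSRS and Braincheck. Define a safety population, since the SAP has only ITT and PP; Adverse Event Assessment already refers to participants exposed to study treatment. Then specify, by arm:

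- **C-SSRS, BL to F1:** number and percentage with worsening (for example, a higher ideation item, new endorsement of item 4 or 5, or new behaviour), a shift table, and the risk difference with 95% CI. State a post-baseline recall window that excludes pre-treatment time; the abbreviations list already includes a C-SSRS follow-up version.
- **Braincheck, BL to F1:** change adjusted for BL with 95% CI, plus the distribution or the proportion who decline by a pre-stated amount, because a mean would miss an effect in about 5%.
- **F2 and F3:** descriptive, by treatment received, separating sham participants who have and have not started open label.

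Add the Stage 1 C-SSRS BL-to-F1 shift table to the DSMB package.

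These are reporting categories and change no clinical rule. The cost is SAP wording and a few descriptive tables from scheduled data. The intervals will be wide, so the results should be presented as estimates and not as powered tests.
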